4.1. Primary endpoint

Difference between the two treatment groups in cumulative number of non-invasive and invasive diagnostic procedures, assessed at 1 year after randomization. NITs include exercise ECG, CCTA, Rb-PET CT, MPI, CMRI and stress echocardiography. Invasive procedures include invasive coronary angiographies (ICA) only.

4.2. Statistical Hypothesis, Model and Method of Analysis

Statistical Hypothesis

The statistical null hypothesis is that there is no difference between a PTP plus CAD-score guided rule-out strategy and a PTP guided strategy alone at one year in reducing diagnostic procedures (π) in patients with symptoms suggestive of stable CAD.

$$H_0: X/\pi_{PTP+CAD-score} = X/\pi_{PTP}$$

The alternate hypothesis is that a PTP plus CAD-score guided rule-out strategy is superior to a PTP guided strategy alone at one year in reducing diagnostic procedures (π) in patients with symptoms suggestive of stable CAD.

$$H_A: X/\pi_{PTP+CAD-score} \neq X/\pi_{PTP}$$

Statistical Model and Method of Analysis

The cumulative numbers of diagnostic test will be assessed using Poisson based test and visually by Nelson-Aalen nonparametric estimator.

Total numbers of patients undergoing diagnostic procedures will be presented as total numbers divided into categories of numbers of procedures: Categories: [0, 1, 2, 3+ diagnostic procedures].

The analyses are performed on **FAS** in accordance with the intention-to-treat principles.

A reduction of 15 % or more in the primary endpoint is regarded as clinically significant.

Sample size

A sample size of 521 provides 80 % power with an alpha significance level of 0.05 for testing superiority in terms of numbers of NIT between the control and intervention group.

The power calculation is based on the study design applicable when the study was initiated (Protocol version 3.0) which reflected the European guidelines from 2013 (Montalescot G *et al.* 2013). Protocol version 4.0 and 5.0 reflects the updated European guidelines from 2019 (Knuuti *et al.* 2019), however, the power calculation remains unchanged and a note provides an explanation for each section below.

The main analysis will be based on intention to treat. The study allows for some degree of cross-overs where patients ruled out instead are crossed-over to a NIT. The power calculation simulates a worst-case scenario where the two groups have the lowest expected difference in number of diagnostic procedures; 0% of patients with DF <15% crossed-over to NIT in the control group and 20% of patients with a CAD-score ruling out obstructive CAD in the intervention crossed-over to NIT.

A reduction of 15% or more in the primary endpoint is regarded as clinically significant. Assuming an alpha significance level of 0.05, a statistical power of 80% and an expected number of NIT/ICA of 0.94 per patient in the standard care group, a sample size of 314 patients in each arm is needed to ascertain superiority of the intervention, in this case an absolute reduction in the primary endpoint of 0.17 NIT/ICA per patient, i.e. number of NIT/ICA.

The expected number of NIT/ICA of 0.94 in the control group and 0.77 in the intervention group is based on the following sequence of assumptions:

- No. of first NITs: n=760 in the control group (all patients with DF-score 15-85%) and n= 610 in the intervention group (all patients with a CAD-score not ruling out CAD + 20% of patients with a CAD-score ruling out CAD).
- No. of second NITs: 10% of first NIT; n=76 in the control group and n=61 in the intervention group.
- No. of ICAs: 10% of total population; n=100 in each group.

Note: the patient pathway is expected to change only slightly due to the updated ESC 2019 guidelines (Knuuti *et al.* 2019). Current data indicates that the number of patients in each arm will increase to 521 for the primary endpoint; which stays within the total number of 2000 patients as described below.

Given the abovementioned assumptions, the mean number of investigations (NITs and ICAs combined) per patient will be 0.94 in group 1 and 0.77 in group 2. A sample size of 314 patients in each arm will then provide 80% power for testing superiority in terms of number of diagnostic procedures for the group with CAD-score stratification compared to the group with DF-score only stratification, at an alpha significance level of 0.05.

The study allows for some degree of cross-overs where patients with PTP or CAD-score ruling out CAD instead are crossed-over to a NIT. The power calculation simulates a worst-case scenario where the two

groups (control and intervention group) have the lowest expected difference in number of diagnostic procedures; 0% of patients with low PTP ruling out CAD (Diamond-Forrester(DF) <15 %) crossed-over to NIT in the control and 20% of patients with a CAD-score ruling out CAD in the intervention group crossed-over to NIT.

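### SAP 4.2 and 4.3 leave the variance of the primary Poisson analysis open; on the plan's own counts a variance = mean standard error would be 18-78% too wide, and the SD behind 314 per arm is unstated

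*SAP*

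**What the plan says.** On the primary analysis, SAP 4.2 states: "The cumulative numbers of diagnostic test will be assessed using Poisson based test and visually by Nelson-Aalen nonparametric estimator". It gives no regression model, effect measure, variance estimator or rule for dispersion. It also plans a table of patients by number of procedures: "Categories: [0, 1, 2, 3+ diagnostic procedures". Section 4.3 uses Poisson regression for the subgroup interactions, again without naming a variance. Section 1 requires every analysis to be stratified by site and PTP, which does not settle the variance.

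On sample size, 4.2 assumes means of 0.94 and 0.77 procedures per patient, a difference of 0.17 and alpha 0.05, and concludes: "A sample size of 314 patients in each arm will then provide 80% power for testing superiority in terms of number of diagnostic procedures". The means come from listed counts. First NITs number 760 in control and 610 in intervention. For the second NITs the text reads "No. of second NITs: 10% of first NIT; n=76 in the control group and n=61 in the intervention group". There are 100 ICAs in each group. No SD or variance is given.

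The same section says these figures reflect protocol version 3.0. It opens with "A sample size of 521 provides 80 % power with an alpha significance level of 0.05", and its note says "Current data indicates that the number of patients in each arm will increase to 521 for the primary endpoint". The rates behind 521 are not given.

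**The concern.** Model-based Poisson, dispersion-scaled Poisson and Poisson with robust variance all satisfy the text, yet they give different primary p-values and intervals. Choosing the variance of the primary test is a matter for the SAP. If it is left open, it can be settled after the data have been seen.

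The planning counts suggest that the choice matters. Most patients are expected to have zero or one procedure, which gives less spread than a Poisson variable with the same mean. The usual default, variance equal to the mean, would then overstate the standard error. The sample-size text points the same way, because 314 per arm cannot be obtained from a variance = mean Poisson comparison. Whoever computed it appears to have used a smaller variance that is not written down.

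At stake are the width of the primary interval and the precision of the interaction tests in 4.3, where information is scarcest.

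**Working it through.** **Inputs (SAP 4.2).** Ten per cent of the population is 100 ICAs, so the counts are per 1000 patients.
- Control: (760 + 76 + 100)/1000 = 0.936, printed as 0.94.
- Intervention: (610 + 61 + 100)/1000 = 0.771, printed as 0.77.
- Difference: 0.17 rounded, 0.165 unrounded.
- Alpha 0.05, power 80%. Two-sided is the main case, because the alternative is written with a not-equal sign.

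**Step 1: try to reproduce 314 with variance = mean.** n per arm = (1.960 + 0.842)² × (m1 + m2)/(m1 − m2)², where (1.960 + 0.842)² = 7.849.
- Rounded: 7.849 × 1.71/0.0289 = 464.
- Unrounded: 7.849 × 1.707/0.027225 = 492.

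Power at 314:
- Rounded: 0.17/√(1.71/314) = 2.304, and Φ(2.304 − 1.960) = 63%.
- Unrounded: 0.165/√(1.707/314) = 2.238, and Φ(2.238 − 1.960) = 61%.
- One-sided: 74% and 72%, with 80% power at about 366 to 389 per arm.

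Log-ratio, square-root, conditional-binomial and simulated versions agree closely. None gives 314.

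**Step 2: the variance that 314 implies.** Common variance = 314 × d²/(2 × 7.849).
- d = 0.17: 0.578, SD 0.76.
- d = 0.165: 0.545, SD 0.74.

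This is 0.68 (rounded) or 0.64 (unrounded) of the mean count.

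**Step 3: the variance that the planning counts imply.** Assume at most two NITs and one ICA per patient. The plan does not say how ICAs overlap with NITs, so the whole range is run. Control, with ICA independent of NIT:
- NIT mean 0.836; mean square 0.684 × 1 + 0.076 × 4 = 0.988; variance 0.988 − 0.836² = 0.289.
- ICA variance 0.1 × 0.9 = 0.090.
- Sum 0.379, against a mean of 0.936.

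Other placements add twice the NIT-ICA covariance. The standard-error ratio compares √(1/m1 + 1/m2) with √(v1/m1² + v2/m2²). The n column uses 7.849 × (v1 + v2)/d², with d = 0.165 and, in brackets, 0.17. Power at 314 uses the same variances and d = 0.165.

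| Where the ICAs fall | Variance, control | Variance, intervention | Poisson SE / true SE (log rate ratio) | n per arm for 80% | Power at 314, true variance |
|---|---|---|---|---|---|
| First in patients without NIT | 0.212 | 0.299 | 1.78 | 147 (139) | 98% |
| Independent of NIT | 0.379 | 0.433 | 1.43 | 234 (220) | 90% |
| Only after a first NIT | 0.432 | 0.519 | 1.32 | 274 (258) | 85% |
| First in patients with a second NIT | 0.564 | 0.621 | 1.18 | 341 (322) | 77% |

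In every row both variances lie below their means (0.936 and 0.771). The average variance of the two arms runs from 0.26 to 0.59, so the 0.545-0.578 behind 314 lies within the range, near its upper end.

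**Step 4: effect on the primary interval at 1000 per arm.** Rate ratio 0.771/0.936 = 0.82.
- Variance = mean: SE √(2.365/1000) = 0.0486, 95% CI 0.75-0.91.
- True variance, ICA independent of NIT: SE 0.0341, CI 0.77-0.88.
- True variance, ICA only after a first NIT: SE 0.0370, CI 0.77-0.89.

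**Step 5: does power suffer?** Variance = mean, two-sided, printed rates (rounded, then unrounded):
- 521 per arm: 84%, 82%.
- 1000 per arm: 98%, 98%.

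**The case against.** A reader might infer from Step 1 that 314 is an arithmetic error and that its real power is 61-63%. The SAP does not support that. It never says that 314 came from a variance = mean formula, and its own counts allow 139 to 341 per arm for 80% power. What is missing is the SD.

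A reader might also infer that the trial is underpowered. It is not. The 314 belongs to protocol version 3.0, the current figure is 521, and about 2000 patients are planned. No decision rests on 314.

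It can also be said that a conservative test does no inferential harm. On these counts this largely stands: with both arms following the control distribution, the true two-sided alpha of the model-based test is at most about 0.012, and each interval in Step 4 excludes 1. What remains is lost precision, and a choice left open in the primary analysis.

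Finally, the under-dispersion is conditional. It rests on version 3.0 planning counts and the cap of two NITs and one ICA, while 4.2 reserves a category for three or more procedures. This objection stands, so the observed dispersion may differ in either direction. It is a reason not to tie the test to variance = mean. The effect on the 4.3 interactions cannot be sized without assuming subgroup shares that the SAP does not give.

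**Conclusion.** The point holds as one of specification and precision. Sections 4.2 and 4.3 name a Poisson analysis without its variance. If the data resemble the planning counts, a variance = mean standard error of the log rate ratio is 18-78% too wide over all ICA/NIT overlaps. It is 32-43% too wide under the two plausible ones (ICA only after a first NIT, or independent of NIT). The test is then conservative. These figures are unstratified, use the unrounded means, and assume at most two NITs and one ICA per patient.

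The pairing of 314 per arm with 80% power is compatible with the plan's counts but not with a variance = mean Poisson test, and the SD that it needs is not stated. The documents do not show that 314 is wrong or that the primary endpoint lacks power.

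**What to change.** In 4.2, specify the primary test as Poisson log-link regression of the 1-year procedure count with robust (sandwich) variance. Include the site and PTP strata that section 1 already requires, test two-sided at 0.05, and report the rate ratio with its 95% CI. Robust variance is suitable whether the observed counts turn out under- or over-dispersed. Use the same variance for the interaction tests in 4.3. In the sample-size text, state the SD (or variance) behind 314.

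The cost is one option in the analysis code and a few lines of SAP text. No extra patients are needed.

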4.3. Subgroup Analysis

We will investigate the effect of a PTP plus CAD-score guided strategy versus a PTP guided strategy across the following pre-specified subgroups:

- PTP ($\leq 5\%$ vs. $>5-15\%$ vs. $>15\%$)
- PTP ($\leq 5\%$ vs. $>5\%$)
- PTP ($\leq 5\%$ vs. $>5-15\%$)
- Age (<65 y vs. ≥ 65 y).
- Sex (female vs. male).
- Hypertension (yes vs. no).
- Dyslipidaemia (yes vs. no).
- Diabetes mellitus (yes vs. no).
- Current/former smoker (yes vs. no).
- Family history of CAD (yes vs. no).
- Body mass index (<30 kg/m 2 vs. ≥ 30 kg/m 2).

Poisson-regression will be used in an interaction analysis. The interaction between the randomization variable and the subgroup variable will be investigated. The subgroup analysis will be made using both FAS and PPS.

5. Key Secondary Objective

The key secondary objective is to investigate if a combined PTP plus CAD-score guided rule-out strategy is non-inferior in terms of major adverse cardiac events (MACE) as compared to a standard PTP guided strategy when selecting patients with suspected stable CAD for NIT.

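### Section 4.3 tests effect modification by age and BMI only through two-level cuts; a continuous interaction term in the same Poisson model would use more of the data if the effect changes gradually

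*SAP*

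**What the plan says.** SAP Section 4.3 lists the pre-specified subgroups for the primary endpoint. Two of them are continuous baseline measures divided once: "Age (<65 y vs. ≥ 65 y" and "Body mass index (<30 kg/m 2 vs. ≥ 30 kg/m 2". On method, the section says "Poisson-regression will be used in an interaction analysis" and "The interaction between the randomization variable and the subgroup variable will be investigated", in both the full analysis set and the per-protocol set. The variable tested is therefore the grouped one.

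No continuous age or BMI term is planned elsewhere in the SAP. Section 7 adds heterogeneity only by site and PTP group. The SAP gives no reason for 65 years or 30 kg/m². It also gives no expected distribution of age or BMI, no interaction size or shape, and no power or significance level for any interaction test.

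**The concern.** A cut at 65 treats a patient of 64 as different from one of 66 but the same as one of 40. If the effect of the CAD-score strategy changes gradually with age or body size, the two-group test ignores the variation within each group and has less chance of detecting the change at the same sample size. The Poisson regression already named can take both variables as measured, so the loss is avoidable.

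What is at stake is the sensitivity of two exploratory tests. The PTP cuts in the same list are a separate matter: PTP drives the diagnostic strategy, and they are not questioned here.

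**Working it through.** The SAP has no figure for these tests to reproduce, so the check asks what the cut costs under stated assumptions.

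**Inputs from the SAP.** Section 4.2: "the mean number of investigations (NITs and ICAs combined) per patient will be 0.94 in group 1 and 0.77 in group 2". Section 1: about 2000 patients, randomised 1:1. The level is borrowed from the primary comparison in Section 4.2 ("Assuming an alpha significance level of 0.05, a statistical power of 80" per cent) and taken as two-sided.

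**Assumptions, not in the SAP.** The modifier is roughly normal, the log rate ratio changes linearly with it, and between 50% and 20% of patients lie above the cut.

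**Step 1: information kept.** With share p above the cut, the fraction kept is φ(z_p)² / [p(1−p)]. At p = 0.5 this is 0.3989²/0.25 = 0.637; at p = 0.2 it is 0.2800²/0.16 = 0.490.

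**Step 2: power after the cut.** Starting from 80% on the full scale, power is Φ[(1.960 + 0.842)·√kept − 1.960].

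| Share above cut | Information kept | Lost | Power with cut | Loss from 80% |
|---|---|---|---|---|
| 50% | 0.637 | 36% | 61% | 19 points |
| 30% | 0.576 | 42% | 57% | 23 points |
| 25% | 0.539 | 46% | 54% | 26 points |
| 20% | 0.490 | 51% | 50% | 30 points |

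**Step 3: size of interaction.** The overall log rate ratio is ln(0.77/0.94) = −0.20. An interaction of 0.10 per SD is half of that for each SD: the rate ratio runs from exp(−0.20 − 0.20) = 0.67 at −2 SD to exp(−0.20 + 0.20) = 1.00 at +2 SD. That is a large interaction. At 0.05 per SD the range is exp(−0.30) = 0.74 to exp(−0.10) = 0.90.

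Take 1000 patients per arm and counts of 0 to 3 drawn as binomial(3, μ/3), so the variance is μ(1 − μ/3). The standard error of the interaction per SD is √[0.6455/(1000·0.94²) + 0.5724/(1000·0.77²)] = 0.0412.

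- 0.10 per SD: 0.10/0.0412 = 2.43, and Φ(2.43 − 1.96) = 68% on the full scale. With the cut, 2.43 is multiplied by √kept, giving 49% (p = 0.5) to 40% (p = 0.2).
- 0.05 per SD: 0.05/0.0412 = 1.21, giving 23% on the full scale and 16 to 14% with the cut.

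Simulations on these settings (Poisson regression, robust variance, main effect 0.1 per SD) gave:

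| Interaction per SD | Full scale | Cut | Gap |
|---|---|---|---|
| 0.10 | about 67–70% | about 44–50% | about 18–26 points |
| 0.05 | about 23–27% | about 15–19% | about 8 points |
| 0 (type I error) | about 5% | about 5% | – |

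If the counts instead had Poisson variance, the standard error would be √(1/940 + 1/770) = 0.0486. By the same formula, power at 0.10 per SD is 54% against 38 to 30%, and at 0.05 per SD 18% against 13 to 11%. The ordering is unchanged.

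**Step 4: the opposite shape.** When the true change is a step exactly at the cut, simulation favours the cut test: 78% against 56% at a 50/50 split and 83% against 61% at 80/20 (Poisson counts), and 73% against 53% with the binomial counts.

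**The case against.** The cuts are fixed in advance, exhaustive and reproducible, and both tests hold their type I error, so nothing here is invalid. That stands.

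The advantage of the full scale depends on shape and size. The SAP supports a gradual change no more than it supports a step, and under a step at the cut the ranking reverses. For modest interactions both tests would usually miss the effect, so the practical gain is small. Both points stand and limit the claim. What remains is that a step exactly at 65 years or 30 kg/m² is a narrow possibility, whereas the continuous term is generally the more efficient test over gradual changes.

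A reader might infer that the plan would present a non-significant interaction as proof of a consistent effect across age or body size. The SAP does not say so: it only says the interaction will be investigated, with no threshold and no rule for reading it. A reader might also take the missing rationale as proof that the cuts are arbitrary. The protocol is not at hand and may give a reason, so the statement is only that the SAP gives none.

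Finally, the section already lists eleven subgroup factors, each in two analysis sets, and the proposal adds spline models for two of them. That is a real but small cost.

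**Conclusion.** The point holds as an optional improvement. For a roughly normal modifier, a log-linear change in effect and splits from 50/50 to 80/20, the cuts discard about 36 to 51% of the information on the interaction. From 80% power, that costs about 19 to 30 points. A single figure of about 20 points would fit only the near-even splits.

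With the SAP's rates and 2000 patients, the gain from the full scale is about 18 to 26 points for a large interaction and about 8 points for one half that size. The absolute power figures also depend on the assumed count variance. All of this rests on distributions and interaction sizes that the SAP does not give.

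The stronger reading, that the planned subgroup tests are wrong or would mislead, is not supported. They are valid, exploratory and unpowered, and neither the primary nor the key secondary analysis depends on them.

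**What to change.** In Section 4.3, make the pre-specified interaction test for age and for BMI the randomisation-by-continuous-variable term in the same Poisson regression, expressed per 10 years and per 5 kg/m². Report a restricted cubic spline interaction alongside. State that the linear term remains the test, and that the spline is used for description if linearity clearly fails. Keep the under/over 65 years and under/over 30 kg/m² groups to display rate ratios.

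The cost is a few lines of SAP text and a few extra models, with no new data. The downsides are an assumption of log-linear modification, lower power if the effect changes abruptly at the cut, and a displayed grouping that differs from the scale of the test, which a footnote should explain.

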5.1. Key Secondary Endpoint

Difference between the two treatment groups in proportion of MACE, assessed at 1 year after randomization. MACE is a composite of all-cause death, non-fatal myocardial infarction, unstable angina pectoris, heart failure, ischaemic stroke, and major complication of cardiovascular procedures or diagnostic testing within 72 hours.

5.2. Statistical Hypothesis, Model and Method of Analysis

Statistical Hypothesis

The statistical null hypothesis is a PTP plus CAD-score guided rule-out strategy is inferior in terms of safety outcomes MACE (π) in patients with symptoms suggestive of stable CAD at one year when using a pre-specified non-inferiority margin (δ) as compared to a standard PTP guided strategy.

$$H_0 = \pi_{PTP+CAD-score} - \pi_{PTP} \geq \delta$$

The alternate hypothesis is that a PTP plus CAD-score guided rule-out strategy is non-inferior to a standard PTP-guided strategy in terms of MACE in patients with symptoms suggestive of stable CAD at one year when using a pre-specified non-inferiority margin (δ).

$$H_A = \pi_{PTP+CAD-score} - \pi_{PTP} < \delta$$

Statistical Model and Method of Analysis

The absolute risk difference between treatment groups will be compared to a non-inferiority margin (δ) of 1.5% using a two-sided 95% confidence interval applying a continuity-corrected modification of the Wilson's score method. Based on previous studies (Therming *et al* 2018) the obstructive CAD prevalence is expected to be 6.5% and the event rate in each group is expected to be 1.3% at 1-year FU.

Moreover, data will be analyzed using stratified proportional hazard Cox regression and visually by Kaplan Meier curves.

Sample size

A sample size of 1914 provides 90% power with an alpha significance level of 0.05 for testing non-inferiority in terms of MACE between the control and intervention group.

This sample size calculation is based on the hypothesis of non-inferiority in terms of MACE in the group of patients with DF-score and CAD-score stratification prior to NIT compared with the group of patients with standard care strategy of DF-score stratification prior to NIT. It is assumed that in the control group, 50% of the patients with a DF-score <15% are ruled out of obstructive CAD without further testing, and 50% are referred for further testing. Based on previous studies (Therming *et al* 2018) the obstructive CAD prevalence is expected to be 6.5% and the event rate in each group is expected to be 1.3% at 1-year FU. The non-inferiority margin is set to 1.5%.

The assumed annual MACE event rates for different patient categories are:

- Clean arteries (CACS=0 and no stenosis): 0.4%

- Non-obstructive CAD: 1.2%
- Diagnosed CAD: 6.9%
- Unobserved CAD: 10.0%

The diagnostic performance of the CAD-score and the DF-score is assumed to be 88.7% and 96.7%, respectively, for sensitivity and 41.5% and 17.9%, respectively, for specificity (Schmidt *et al* 2019). The weighted average for sensitivity and specificity of the combined NIT battery is assumed to be 85.6% and 80.2%, respectively, assuming a distribution of exercise ECG, stress echo, MPI and CCTA as in Therming *et al* 2018 and diagnostic performance for each test as in the ESC 2013 guidelines (Montalescot *et al* 2013).

With the abovementioned assumptions a sample size of 1914 provides 90% power for testing non-inferiority in terms of MACE between the two testing strategies, at an alpha significance level of 0.05.

Note: the MACE event rate is not expected to change due to the updated ESC 2019 guidelines (Knuuti *et al*. 2019), thus the power calculation related to the MACE endpoint remains unchanged.

6. Other Secondary Objectives

Other secondary objectives are to compare the two treatment arms with respect to:

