6.5.1 Objectives	13
6.5.2 Endpoints.....	14
6.5.3 Statistical Hypothesis, Model and Method of Analysis	14
6.6. Quality of Life	14

6.6.1 Objective.....	14
6.6.2 Endpoint	15
6.6.3 Statistical Hypothesis, Model and Method of Analysis	15
7. Sensitivity Analysis.....	15
8. Missing Data	15
9. References	15

1. Background and Study Design

The FILTER-SCAD trial is a randomized, controlled, multicentre, superiority trial with two parallel groups investigating the use of the acoustic measured risk score (CAD-score) for obstructive coronary artery disease (CAD) for ruling out CAD as compared to current standard diagnostic strategy in patients with symptoms suggestive of CAD.

Approximately 2000 patients with symptoms suggestive of CAD referred for outpatient assessment are expected to be enrolled at 5 study sites in Denmark and 1 in Sweden. The subjects will be randomized 1:1 to either 1) standard diagnostic strategy i.e. pre-test probability (PTP) stratification followed by non-invasive test (NIT), if indicated (control group), or (2) PTP plus CAD-score stratification followed by NIT, if indicated (intervention group). Randomization is stratified according to study site and PTP. Given the stratified design, all analyzes are carried out stratified by site and PTP.

2. Analysis Datasets

All patients from whom written informed consent are obtained will be included in the **full analysis set (FAS)**. Subjects will be analysed according to the allocated randomization group in accordance with the intention-to-treat principles.

The **per protocol set (PPS)** will include the subjects from the FAS who did *not* have one of the following major protocol violations:

- inclusion criteria not met
- exclusion criteria met
- no PTP calculation
- no CAD-score measurement (intervention group only).

Patients who did not receive the randomly allocated CAD-score measurement will be included and analysed in the control group (per protocol analysis).

The **screened analysis set (SAS)** will include all screened patients who receive a subject number.

3. Demographics and Baseline Characteristics

Continuous variables will be presented as mean and standard deviation for variables following a normal distribution or as median with interquartile range if showing a skewed distribution. Categorical variables will be presented as frequencies and percentages. Categorical data will be compared using Fisher's exact

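### The MACE non-inferiority test names no analysis set, and the per-protocol set that would check it both excludes unscored intervention patients and counts them as controls

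*SAP*

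**What the plan says.** Section 2 defines the FAS as all consented patients, analysed as randomised under intention to treat. The PPS is the FAS without four listed major violations, one of which is a missing CAD-score, for the intervention group only. The sentence after the list says: "Patients who did not receive the randomly allocated CAD-score measurement will be included and analysed in the control group (per protocol analysis").

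Section 5.2 tests MACE on the absolute risk difference: "The absolute risk difference between treatment groups will be compared to a non-inferiority margin" of 1.5 points, "using a two-sided 95% confidence interval applying a continuity-corrected modification of the Wilson's score method". It gives the hypotheses, margin, interval, Cox model and sample size, but no analysis set.

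Other sections do name one:
- Section 3 (baseline): FAS, PPS and the screened set (SAS).
- Section 4.2 (primary endpoint): FAS.
- Section 4.3: "The subgroup analysis will be made using both FAS and PPS".
- Section 7 (sensitivity analysis of all endpoints, patients enrolled under protocol versions 4.0 and 5.0): PPS and SAS.

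Sections 6.1 to 6.6 name none. Nothing says how a PPS result for MACE bears on the conclusion if it differs from the FAS result.

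**The concern.** This is the SAP's only non-inferiority test and it carries the safety conclusion. A per-protocol result is usually set beside the intention-to-treat result, because departures from the allocated strategy can hide a difference. That check needs a PPS that keeps patients in their randomised arm.

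This one does not. An intervention patient without a CAD-score is out of the set under the violation list and in the control arm under the next sentence. Two programmers could build two different sets from the same text. If the second sentence is followed, the comparison is no longer between randomised groups: any MACE among these patients leaves the intervention arm and is added to control. With few events expected, that can decide whether the upper limit falls below 1.5 points.

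**Working it through.** **Inputs from Section 5.2.** Margin 1.5 points; "the event rate in each group is expected to be 1.3% at 1-year FU"; two-sided 95% interval; total sample size 1914, that is 957 per arm at 1:1. Expected events per arm: 957 × 0.013 = 12.4, or 1000 × 0.013 = 13 if 2000 are enrolled.

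**The plan's own figure.** n per arm = (z₁₋α + z₀.₉₀)² × 2 × 0.013 × 0.987 / 0.015². One-sided α = 0.05 gives 977 per arm, 1954 in total, about 2% above the stated 1914. The figure is reproduced on that reading. (One-sided 0.025, which matches the planned two-sided 95% interval, gives 1199 per arm, 2398 in total. That is a separate matter.) Naming the analysis set does not change this calculation.

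**Interval.** I read the method as continuity-corrected Wilson limits for each arm, combined for the difference (Newcombe), unstratified. With z = 1.96 and p = x/n:

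- u = [2np + z² + 1 + z√(z² + 2 − 1/n + 4p(n(1−p) − 1))] / [2(n + z²)]
- l = [2np + z² − 1 − z√(z² − 2 − 1/n + 4p(n(1−p) + 1))] / [2(n + z²)]
- Upper limit U = (p₁ − p₀) + √[(u₁ − p₁)² + (p₀ − l₀)²]

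For 17/1000 v 13/1000: p₁ − p₀ = 0.400, u₁ = 2.767, l₀ = 0.724 (all in per cent), so U = 0.400 + √(1.067² + 0.576²) = 1.61.

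**Illustration A: 1000 per arm, 50 intervention patients without a CAD-score.** All counts are assumed.

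| Set | Intervention v control | U (points) | Below 1.5? |
|---|---|---|---|
| FAS | 17/1000 v 13/1000 | 1.61 | no |
| Moved to control, with 2 events | 15/950 v 15/1050 | 1.38 | yes |
| Moved, with 1 event | 16/950 v 14/1050 | 1.59 | no |
| Moved, with 0 events | 17/950 v 13/1050 | 1.80 | no |
| Excluded, with 2 events | 15/950 v 13/1000 | 1.498 | yes, barely |

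**Illustration B: 957 per arm, 48 (5%) without a CAD-score.** All counts are assumed.

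| FAS events | FAS U | Events among the 48 | U if moved | U if excluded |
|---|---|---|---|---|
| 15 v 12 | 1.52 (fails) | 2 | 1.26 (passes) | 1.39 (passes) |
| 14 v 12 | 1.40 (passes) | 0 | 1.57 (fails) | 1.52 (fails) |

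**Direction of the bias.** Hold the true FAS difference at the margin (2.8% v 1.3%) and move 48 of 957 patients with risk r. The difference becomes (957 × 0.028 − 48r)/909 − (957 × 0.013 + 48r)/1005. For r = 1.3%, 2.6%, 3.9% and 5.2% it is 1.58, 1.45, 1.32 and 1.19 points. Setting the expression equal to 1.5 points gives r of about 2.1%, close to the midpoint of the two arm rates. Below that, moving patients works against non-inferiority; above it, in favour. The SAP gives neither the expected share without a CAD-score nor their risk, so the direction cannot be known in advance.

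**The case against.** The strongest reply is that the FAS is already the default. Section 2 attaches intention to treat to the FAS, Section 4.2 says the main analysis follows it (within the primary endpoint's sample size text), and the silence of Sections 6.1 to 6.6 fits a general FAS default with exceptions stated where they apply. This largely stands. The omission in 5.2 alone is a gap in explicitness, and the text does not offer a free choice of set.

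It can also be said that the PPS reaches MACE only through Section 7, as a sensitivity analysis in later enrolees, and that the two sentences in Section 2 could be reconciled as removal from the intervention arm followed by counting in control. The first limits the reach of the problem. The second removes the contradiction but leaves a non-randomised comparison under a per-protocol label.

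A reader might infer more: that both sets lean towards non-inferiority. The documents do not support this. The PPS can lean either way, as shown above. For the FAS, the argument would be that 20% dilution turns a true excess of 1.5 points into 1.2 and raises the chance of a false claim from 1.9% to 5.4% (1000 per arm). But the scenario with "20% of patients with a CAD-score ruling out obstructive CAD in the intervention crossed-over to NIT" belongs to the primary endpoint's power calculation and covers only patients ruled out by the CAD-score, not the whole arm. Cross-over is allowed, and the trial compares strategies. If the delivered strategies differ by 1.2 points, that is inside the margin and the claim is not false. Cross-over is also not a PPS violation, so these patients stay in both sets, and requiring both sets to pass would not remove dilution.

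**Conclusion.** The point holds in limited form. Section 5.2 should name its analysis set, although the FAS is the sensible reading. The firmer defect is in Section 2: the PPS rule contradicts itself, and its second half breaks randomisation in a set that Section 7 applies to MACE.

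The size is a matter of one or two events out of about 12 to 13 expected per arm. In the illustrations the upper limit moves from 1.61 to 1.38 or 1.80, and from 1.40 to 1.57, across a margin of 1.5 points. These results rest on assumed event counts, an assumed 5% without a CAD-score, and the unstratified interval. They show that the verdict can reverse, not how often it would. If few patients lack a score, the effect is small.

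Excluding unscored patients instead of moving them does not make the PPS neutral: it can also cross the margin (1.498 in illustration A, 1.52 in B). That is a reason to let the FAS govern and to treat the PPS as supportive. A rule that both sets must pass is an optional convention; nothing in the SAP makes it necessary.

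**What to change.** 1. In Section 5.2, state that non-inferiority for MACE is concluded from the FAS, with patients in their randomised arm, and that the same analysis is run in the PPS as support, with its consistency with the FAS result reported.
2. In Section 2, delete the sentence that places unscored intervention patients in the control group. The PPS then keeps randomised arms and excludes these patients, as its violation list already says. This also settles the subgroup and sensitivity analyses that use the PPS.
3. Report the number of intervention patients without a CAD-score and their MACE count, so that a reader can see how much the exclusion matters.

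The change should be made before the outcome data are unblinded. It costs a few lines of SAP text, one extra run of the same analysis and a slightly smaller PPS. The sample size calculation is not affected.
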